6 STUDY PROCEDURES

Study staff will always be present to assist and ensure subject safety. There will be a minimum of 2 staff members to assist subjects during assessments, and a security officer will be in the unit supervising subjects while intoxicated. If a subject becomes a danger to themselves or others, they will be isolated and may be physically restrained using soft hospital-approved restraints.

During the study, subjects will stay in private rooms and not be sharing rooms. Some procedures (ie, digital photography) will occur outside their room, and subjects will be accompanied by staff throughout the protocol assessments. Throughout the study, subjects will be instructed to remain in their personal space and continuously supervised by multiple staff.

Staff will always be present to monitor, assist, and ensure subject safety. There will be a minimum of 2 staff members to assist subjects during assessments. Subjects will be sequestered to their private rooms while intoxicated. Staff will be available to escort subjects to the restroom. Each restroom is equipped with an alarm. Arrangements could also be made for a bedside commode and urinals as needed.

Study procedures will follow the Schedule of Procedures ([Appendix A](#)).

7 ENDPOINTS

The study is not formally powered as all endpoints are exploratory in nature.

The primary exploratory efficacy endpoints include the following:

- Assessment of symptoms using the Global Impression Visual Analog Scale, CGI-Impairment Severity Scale, CGI-Improvement Scale, and the Alcohol Toxicity Symptom Scale;
- Assessment of signs, determined by evaluation of the following:
 - Objective flushing and ocular redness scales (via digital photography); and
 - Proprioception tests (Romberg Test [time of up to 60 seconds], One Leg Stand Test [time of up to 60 seconds], Straight-Line Heel-to-Toe Test [up to 100 steps]).
- Assessment of ADX-629 activity, determined by evaluation of the following PD markers, for both treatment periods, on Day 1 pre-dose, on Day 1 one hour after the target BAC is achieved, and on Day 2 one hour after the last dose of study drug:
 - HNE, acetaldehyde, malondialdehyde-acetaldehyde adduct (MAA), and MDA plasma concentrations; and
 - Plasma cytokine concentrations including, but not limited to, interferon gamma, IL-1b, IL-10, IL-12, and IL-17.

7.1 Symptom Assessments

7.1.1 Global Impression Visual Analog Scale

For both treatment periods, subjects will be asked to assess the extent of their symptoms at the timepoints indicated in the Schedule of Procedures ([Appendix A](#)) utilizing the Global Impression Visual Analog Scale ([Appendix C](#)). The extent of symptoms will be assessed on a 100-point scale from no symptoms to maximal symptoms.

7.1.2 Clinical Global Impression-Impairment Severity and -Improvement Scales

For both treatment periods, subjects will be asked to rate their overall severity of impairment and improvement in symptoms at the timepoints indicated in the Schedule of Procedures ([Appendix A](#)) utilizing the CGI-Impairment Severity and CGI-Improvement Scales ([Appendix C](#)).

Overall severity of impairment will be assessed on a 7-point scale from no impairment to very severe impairment.

For both treatment periods on Day 2, overall improvement of symptoms (relative to symptoms upon waking on Day 2) will be assessed on a 7-point scale from very much worse to very much improved. The CGI-Improvement Scale will only be administered on Day 2 at approximately 7 am, 10 am, and 1 pm.

7.1.3 Alcohol Toxicity Symptom Scale

The subjects will be asked to score their symptoms at the timepoints indicated in the Schedule of Procedures ([Appendix A](#)) utilizing the Alcohol Toxicity Symptom Scale ([Appendix C](#)). This scale will include assessment of hydration status, fatigue, headache, and nausea including inquiries about vomiting, muscle weakness, ability to concentrate, light and sound sensitivity, sweating,

trembling/shaking, and mood such as anxiety and/or depression. For the 0 to 10 scale in the Alcohol Toxicity score, subjects will be instructed that a “10” implies that the subject would have to call off from work and/or be unable to perform normal activities until recovered, due to that specific symptom. A “5” implies that the subject could perform normal activities, such as work, but with a decreased performance level. A “0” implies that there would be no impact on normal activities at all. For the thirst/dehydration and sweating category, subjects will rank their symptom on a scale of 0 to 10 based on prior, subjective experience.

The vomiting category within the Alcohol Toxicity Symptom Scale is meant to measure the secondary effects of ethanol toxicity (ie, from acetaldehyde) as opposed to effects related to euphoria or central nervous system depression. Vomiting will be evaluated separately with individual AEs. A positive vomiting score will be documented if vomiting has occurred 8 to 12 hours after BAC is met. Vomiting observed 0 to 8 hours after BAC is met will not be included in the toxicity reporting.

7.2 Sign Assessments

7.2.1 Objective Flushing and Ocular Redness

Subjects will be evaluated for signs of objective flushing and ocular redness via digital photography at the timepoints indicated in the Schedule of Procedures ([Appendix A](#)).

7.2.2 Proprioception Tests

Subjects will be evaluated for proprioception using the Romberg Test, One Leg Stand Test, and Straight-Line Heel-to-Toe Test at the timepoints indicated in the Schedule of Procedures ([Appendix A](#)).

The Romberg Test will be conducted in a standing position with the subject’s feet together, arms by the side, and eyes closed. Subjects will be evaluated to determine how long they can stand without movement, (eg, any part of body movement, including eyes opening). Slight swaying is allowed. The length of time the subject is able to stand without movement will be recorded.

The One Leg Stand Test will be conducted in a standing position with one of the subject’s legs raised slightly off the ground. The length of time the subject is able to stand in this position will be recorded.

The Straight-Line Heel-to-Toe Test will be conducted with the subject walking heel-to-toe on a demarcated floor that will include a walking line and an “out-of-bounds” area marked 3 to 6 inches outside of the walking line. The number of steps the subject is able to take without stepping “out-of-bounds” will be recorded.

7.3 Pharmacodynamic Assessments

Blood samples for PD markers, such as plasma HNE, plasma acetaldehyde, plasma MAA, plasma MDA, and plasma cytokine concentrations (including, but not limited to, interferon gamma, IL-1b, IL-10, IL-12, and IL-17) will be collected for both treatment periods on Day 1 pre-dose, on Day 1 one hour after the target BAC is achieved, and on Day 2 one hour after the last dose of study drug.

8 SAFETY ASSESSMENTS

The primary safety endpoint is the safety and tolerability of ADX-629, determined by evaluation of the following:

- AEs;
- Physical examinations;
- Vital signs (blood pressure, heart rate, respiratory rate, temperature, and oxygen saturation);
- 12-lead electrocardiograms (ECGs);
- BAC;
- Clinical laboratory assessments (including chemistry, hematology, and urinalysis); and
- Lipid panel evaluations.

8.1 Adverse Events

An AE is defined as any untoward medical occurrence in a clinical investigation subject administered a pharmaceutical product, which does not necessarily have a causal relationship with this treatment. An AE can therefore be any unfavorable and/or unintended sign (including an abnormal laboratory finding), symptom, or disease temporally associated with the use of an investigational medicinal product, whether or not related to the investigational medicinal product. All AEs, including observed or volunteered problems, complaints, or symptoms, are to be recorded on the appropriate eCRF.

AEs, which include clinical laboratory test variables, will be monitored and documented from the time of informed consent until study participation is complete. SAEs occurring from the time of informed consent until 30 days following the last administration of study drug will be monitored and documented. Subjects should be instructed to report any AE that they experience to the Investigator, whether or not they think the event is due to study treatment. Beginning at Screening, Investigators should make an assessment for AEs at each visit and record the event on the appropriate AE eCRF.

Wherever possible, a specific disease or syndrome rather than individual associated signs and symptoms should be identified by the Investigator and recorded on the eCRF. However, if an observed or reported sign or symptom is not considered a component of a specific disease or syndrome by the Investigator, it should be recorded as a separate AE on the eCRF. Additionally, the condition that led to a medical or surgical procedure (eg, surgery, endoscopy, tooth extraction, or transfusion) should be recorded as an AE, not the procedure itself.

Any medical condition already present at Screening should be recorded as medical history and not be reported as an AE unless the medical condition or signs or symptoms present at baseline changes in severity, frequency, or seriousness at any time during the study. In this case, it should be reported as an AE.

Clinically significant abnormal laboratory or other examination (eg, ECG) findings that are detected during the study or are present at Screening and significantly worsen during the study should be reported as AEs, as described below. The Investigator will exercise his or her medical and scientific judgment in deciding whether an abnormal laboratory finding or other abnormal assessment is clinically significant. Clinically significant abnormal laboratory values occurring

during the clinical study will be followed until repeat tests return to normal, stabilize, or are no longer clinically significant. Abnormal test results that are determined to be an error should not be reported as an AE. Laboratory abnormalities or other abnormal clinical findings (eg, ECG abnormalities) should be reported as an AE if any of the following are applicable:

- If an intervention is required as a result of the abnormality;
- If action taken with the study drug is required as a result of the abnormality; or
- Based on the clinical judgment of the Investigator.

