8.1.4 Adverse Events of Special Interest

There are no AEs of special interest defined for this study.

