3.4 Efficacy Assessment

Efficacy assessment will be summarized on the ITT Population.

The primary exploratory efficacy endpoints will include the following:

Assessment of symptoms

- Global Impression Visual Analog Scale
- Clinical Global Impression (CGI)-Impairment Severity Scale

- CGI-Improvement Scale
- Alcohol Toxicity Symptom Scale (thirsty or dehydrated, more tired than usual, headache, nausea, vomiting, weak, difficulty concentrating, sensitive to light and sound, sweating, anxious, depressed, trembling or shaking)

Assessment of signs

[figure not shown]
- Objective flushing and ocular redness scales (via digital photography)
- Proprioception tests (Romberg Test [time of up to 60 seconds], One Leg Stand Test [time of up to 60 seconds], Straight-Line Heel-to-Toe Test [up to 100 steps]).

Assessment of ADX-629 pharmacodynamic activity

- PD markers: HNE, acetaldehyde, malondialdehyde-acetaldehyde adduct (MAA), and MDA plasma concentrations;
- Plasma cytokine concentrations including, but not limited to, interferon gamma, IL-1b, IL-10, IL-12, and IL-17

Factors:

- Timepoint
- Baseline
- BAC
- Number of bodyweight-standardized drinks consumed
- Emesis volume
- Emesis 8-12 hours after first drink (binary)

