3.5.1 Adverse Events (AEs)

All AEs will be coded to system organ class and preferred term using MedDRA version 24.0. Treatment-emergent adverse events (TEAEs) are defined as AEs that start after the first dose of study drug.

An overview of AEs will be provided including counts and percentages of subjects (and event counts) with the following:

[figure not shown]
- Any AEs
- Any AEs related to COVID-19
- Any TEAEs (overall and by maximum severity)
- Any study drug related TEAEs (overall and by maximum severity)
- Any serious AEs (SAEs)
- Any treatment-emergent serious AEs (TESAEs)
- Any TEAEs leading to discontinuation of study
- Any AEs leading to death

Counts and percentages of subjects (and event counts) will also be presented by system organ class and preferred term for each of the categories in the overview.

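### The syndrome-first adverse event rule in Protocol 8.1 lets ethanol symptoms be merged under one intoxication-type term and is not reconciled with the vomiting rule in 7.1.3

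*Protocol*

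**What the plan says.** Protocol 8.1 sets three rules for what goes on the AE form.

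- Symptoms count as events: "All AEs, including observed or volunteered problems, complaints, or symptoms, are to be recorded on the appropriate eCRF".
- A syndrome is preferred to its parts: "Wherever possible, a specific disease or syndrome rather than individual associated signs and symptoms should be identified by the Investigator".
- The exception is a sign or symptom that "is not considered a component of a specific disease or syndrome by the Investigator, it should be recorded as a separate AE".

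Protocol 7.1.3 treats vomiting differently. It is scored on the Alcohol Toxicity Symptom Scale only if it occurs 8 to 12 hours after BAC is met. For the earlier window the text is "Vomiting observed 0 to 8 hours after BAC is met will not be included in the toxicity reporting", and the section adds "Vomiting will be evaluated separately with individual AEs".

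Protocol 8.1.4 states "There are no AEs of special interest defined for this study". That is not an error, but it means no list protects particular symptoms from being merged. SAP 3.5.1 builds its tables on the recorded terms: "Counts and percentages of subjects (and event counts) will also be presented by system organ class and preferred term". SAP 3.5 summarises all safety data by treatment sequence and in total.

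**The concern.** The syndrome rule is ordinary AE practice when a disease is discovered during a trial. Here the syndrome is induced by design, in every subject, in both periods (Protocol 3.1). An investigator can reasonably regard nausea, dizziness or vomiting on Day 1 as a component of intoxication. The exception then does not apply, and one term may stand for all of them. Nothing in the supplied text says whether expected ethanol effects are AEs, which term is acceptable, or which symptoms must stay separate. The choice may therefore differ between subjects, or between the two periods of one subject.

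This matters because the primary objective is the interaction between ADX-629 and ethanol, and AEs come first in the primary safety endpoint. An interaction could show as more frequent, earlier or more severe individual symptoms on ADX-629. A merged term carries one onset, one grade and one causality call. Under Protocol 8.1.3 a related event requires that no other cause can be identified, and an event named after alcohol already names another cause.

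**Working it through.** There is no figure in the plan to reproduce: the sample of about 30 is stated not to rest on statistical considerations, and no symptom rates are given. The check has four steps.

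**1. What is captured outside the AE form.** The symptoms are those in inclusion criterion 4, plus vomiting. The scale items are those in SAP 3.4: "Alcohol Toxicity Symptom Scale (thirsty or dehydrated, more tired than usual, headache, nausea, vomiting, weak, difficulty concentrating, sensitive to light and sound, sweating", followed by anxious, depressed, and trembling or shaking (12 in all).

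| Symptom | Other capture |
|---|---|
| Headache, nausea, fatigue | Own scale items |
| Flushing | Digital photography (Protocol 7.2.1) |
| Confusion/disorientation | Only approximately, by the concentration item |
| Diarrhea, dizziness, nystagmus | No scale item |
| Vomiting 8 to 12 h after BAC is met | Scale item |
| Vomiting 0 to 8 h after BAC is met | Excluded from the scale |

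Blood pressure, heart rate and oxygen saturation are also measured about every 30 minutes after alcohol until BAC returns to 0.11 g/100 mL (Protocol 8.8).

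**2. Whether the SAP emesis factors fill the early-vomiting gap.** SAP 3.4 lists emesis volume and a binary indicator for 8-12 hours after the first drink, both as factors rather than outcomes. If target BAC is reached t hours after the first drink, the indicator covers 8 − t to 12 − t hours after BAC is met. Assuming that the 4-hour window for reaching target BAC starts at the first drink, t is at most 4, so coverage starts no earlier than 8 − 4 = 4 hours after BAC. The first 4 hours after target BAC are therefore in neither the indicator nor the scale. Only the volume record, for which no window is given, may cover them. The two clocks (first drink, and BAC met) also need reconciling.

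**3. Dilution from merging (assumed rates).** Take 12 independent symptoms. One occurs in 30% of subjects on one treatment and 60% on the other; the other 11 occur at rate b on both. Recorded individually, 30 subjects give 30 × 0.30 = 9 versus 30 × 0.60 = 18, a difference of 30 points. Merged fully into one term, the difference in any event is (1 − b)^11 × 30 points:

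| b | (1 − b)^11 | Difference, points |
|---|---|---|
| 10% | 0.3138 | 9.4 |
| 20% | 0.0859 | 2.6 |
| 30% | 0.0198 | 0.6 |
| 50% | 0.0005 | 0.01 |

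If a share f of subjects is merged, equally on both treatments, the symptom-level difference is 30 × (1 − f): 22.5, 15 and 7.5 points at f = 25%, 50% and 75%. If f differs between treatments, the table can also show a difference that is only one of recording.

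**4. What the planned tables can show.** Each sequence contains both treatments. With the same assumed rates and independent periods, the expected share of subjects ever having the symptom is 1 − 0.70 × 0.40 = 0.72 in AB and 0.72 in BA. Without period or carryover effects the two sequences have the same expectation whatever the drug does. Symptom-level recording alone would therefore not bring an ADX-629 versus placebo difference into these tables.

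**The case against.** The strongest reply is that the text does not require merging. Protocol 8.1 says symptoms are to be recorded, it leaves attribution to a syndrome to the investigator, and neither document uses an intoxication term for an AE. A reader might infer that every ethanol symptom will disappear into one event. That is a prediction of behaviour, and the documents support only that merging is allowed. This part of the reply stands.

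A reader might also infer that 8.1 contradicts 7.1.3. It does not have to: 7.1.3 concerns vomiting alone and can be read as a specific exception to a general rule. The passages are unreconciled, because neither refers to the other and a site following 8.1 literally could merge vomiting.

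Nor would symptom-level differences be lost from the trial as a whole. Most named symptoms are scored, photographed or measured elsewhere. Protocol 8.10 adds symptom-based examinations around each dose, a merged AE keeps a severity grade that SAP 3.5.1 tabulates by maximum, and source notes may allow partial recovery. This also stands, and it limits the point to the items in the verdict.

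Finally, a dramatic example can be built: 9 versus 0 discordant pairs for vomiting gives an exact two-sided p of 2 × 0.5^9 = 0.0039, against p = 1 if all 30 are merged in both periods. The arithmetic is right, but the counts are invented, partial merging is ignored and no AE test is planned.

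The Study Procedures Manual, the eCRF instructions and a readable Schedule of Procedures were not available. They may already address the recording of ethanol effects.

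**Conclusion.** The point holds in a limited form. Applied to deliberate intoxication, Protocol 8.1 permits inconsistent or merged recording of ethanol symptoms, and it is not reconciled with the reliance on individual AEs for vomiting in 7.1.3. What is specifically at risk is early vomiting as a reported outcome, diarrhea, dizziness and nystagmus, and the symptom-level AE attributes of onset, severity and causality.

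The size cannot be taken from the documents. Under the assumed rates the loss is proportional to the share merged, and close to complete only if merging is general and other symptoms are common. The exploratory symptom scales, photographs and vital signs are unaffected. This is a worthwhile clarification of moderate weight and does not undermine the design. It should be made together with a change in how AEs are tabulated, since summaries by sequence would not separate the treatments even with perfect recording.

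**What to change.** **Protocol 8.1.** Add an exception: signs and symptoms occurring after study ethanol, at least vomiting and the symptoms listed in inclusion criterion 4, are each recorded as their own AE with onset time and severity, and are not replaced by a term such as *alcohol intoxication* or *hangover*. State that this reconciles 8.1 with 7.1.3. Repeat it in the eCRF completion guidance and site training.

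**SAP 3.5 and 3.5.1.** Tabulate these preferred terms as a pre-specified group by treatment received at onset (ADX-629 or placebo), in addition to sequence and total. State how events starting in the washout are assigned.

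**SAP 3.4.** Align the time origin of the emesis indicator with Protocol 7.1.3, or explain why it differs.

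The cost is one protocol sentence, a completion note, training, more AE records for about 30 subjects at one site, and busier AE tables. If recording has already begun, the exception cannot restore symptom terms that were never entered, so the SAP should then say which records predate it.

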8.1.1 Adverse (Drug) Reaction

All noxious and unintended responses to a medicinal product related to any dose should be considered an adverse drug reaction. “Responses” to a medicinal product means that a causal relationship between a medicinal product and an AE is at least a reasonable possibility, ie the relationship cannot be ruled out.

8.1.2 Unexpected Adverse Drug Reaction

An unexpected adverse drug reaction is defined as an adverse reaction, the nature or severity of which is not consistent with the applicable product information.

8.1.3 Assessment of Adverse Events by the Investigator

The Investigator will assess the severity (intensity) of each AE as mild, moderate, or severe, and will also categorize each AE as to its potential relationship to study drug using the categories of yes or no.

Assessment of severity:

The severity of all AEs should be graded according to the latest version of Common Terminology Criteria for Adverse Events (CTCAE). For those AE terms not listed in the CTCAE, the following grading system should be used:

- CTCAE Grade 1: Mild; asymptomatic or mild symptoms; clinical or diagnostic observations only; intervention not indicated;
- CTCAE Grade 2: Moderate; minimal local or noninvasive intervention indicated; limiting age-appropriate instrumental activities of daily living;
- CTCAE Grade 3: Severe or medically significant but not immediately life-threatening; hospitalization or prolongation of hospitalization indicated; disabling; limiting self-care activities of daily living;
- CTCAE Grade 4: Life-threatening consequences; urgent intervention indicated; and
- CTCAE Grade 5: Death related to the AE.

Causality assessment:

The relationship of an AE to the administration of the study drug is to be assessed according to the following definitions:

No (unrelated, not related, unlikely to be related) – The time course between the administration of study drug and the occurrence or worsening of the AE rules out a causal relationship and another cause (concomitant drugs, therapies, complications, etc) is suspected.

Yes (possibly, probably, or definitely related) – The time course between the administration of study drug and the occurrence or worsening of the AE is consistent with a causal relationship and no other cause (concomitant drugs, therapies, complications, etc) can be identified.

The definition implies a reasonable possibility of a causal relationship between the event and the study drug. This means that there are facts (evidence) or arguments to suggest a causal relationship.

The following factors should also be considered:

- The temporal sequence from study drug administration;

The event should occur after the study drug is given. The length of time from study drug exposure to event should be evaluated in the clinical context of the event.

- Underlying, concomitant, intercurrent diseases;

Each report should be evaluated in the context of the natural history and course of the disease being treated and any other disease the subject may have.

- Concomitant drug;

The other drugs the subject is taking or the treatment the subject receives should be examined to determine whether any of them might be recognized to cause the event in question.

- Known response pattern for this class of study drug;

Clinical and/or preclinical data may indicate whether a particular response is likely to be a class effect.

- Exposure to physical and/or mental stresses; and

The exposure to stress might induce adverse changes in the recipient and provide a logical and better explanation for the event.

- The pharmacology and PK of the study drug;

The known pharmacologic properties (absorption, distribution, metabolism, and excretion) of the study drug should be considered.

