2 STUDY OBJECTIVE

2.1 Primary Objective

The primary objective is to assess the interaction between ADX-629 and ethanol while exploring the safety, tolerability, and activity of ADX-629 in subjects with elevated ethanol levels.

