- Day 1: 1 dose of study drug will be administered at approximately 4:30 pm followed by standardized ethanol consumption as outlined in the manual, and then 1 dose of study drug will be administered at approximately 7 pm followed by continued standardized ethanol consumption to reach a target blood alcohol concentration (BAC) of 0.14 g/100 mL, measured via breathalyzer. For more details on the breathalyzer measurements, refer to the Study Procedures Manual. Symptom and sign assessments (with the exception of the CGI-Improvement Scale) will be evaluated and should be completed as soon as practical after target BAC is reached. Study procedures will be reviewed for randomized subjects, and, based on the emerging data, the standardized ethanol solution and/or BAC testing methods may be modified as needed to ensure target BAC is reached within a 4-hour window for the remaining subjects; and

Note: Subjects will be observed for safety during the treatment periods by study site personnel who will be present to assist subjects at all times; there will be a minimum

requirement of at least 2 study site personnel to assist subjects during their assessments. Safety measures will be in place to prevent falling.

Note: Ethanol will be administered in a standardized oral solution. For more details on the consumption guidelines, refer to the Study Procedures Manual.

- Day 2: 1 dose of study drug will be administered at approximately 8 am, and symptom and sign assessments (including the CGI-Improvement Scale) will be completed at approximately 7 am, 10 am, and 1 pm. Subjects will be discharged from the study site after completion of study procedures (approximately 12 hours after the last dose of study drug). Prior to discharge, vital signs will be measured. Subjects will have to achieve a BAC of 0.00 g/100 mL as measured by a breathalyzer before discharge.
- A follow-up telephone call will occur 3 days (± 1 day) after completion of Treatment Period 2.

For subjects who are withdrawn from the study prior to completion, study procedures will be performed at an Early Termination Visit.

There will be at least a 14-day washout period between the last dose of study drug in Treatment Period 1 and the first dose of study drug in Treatment Period 2. Subjects will need to refrain from drinking alcohol during the washout period.

An individual subject's participation in the study is estimated to be approximately 41 days.

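### The Yes and No causality definitions in Protocol 8.1.3 are not exhaustive: an adverse event with drug-compatible timing and another identified cause, such as the study ethanol, meets neither

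*Protocol*

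**What the plan says.** Protocol 8.1.3 has the investigator put every AE into one of two causality categories, Yes or No. Each category has a label and a definition, and each definition joins a timing condition to a condition on other causes with *and*.

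- Yes is labelled "Yes (possibly, probably, or definitely related" and applies when the time course "is consistent with a causal relationship and no other cause (concomitant drugs, therapies, complications, etc) can be identified".
- No has a label that runs from unrelated to unlikely, and applies when the time course "rules out a causal relationship and another cause (concomitant drugs, therapies, complications, etc) is suspected".

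The sentence that follows reads: "The definition implies a reasonable possibility of a causal relationship between the event and the study drug". A list of factors to weigh comes next. Under concomitant drugs, it says that the subject's other drugs and treatment "should be examined to determine whether any of them might be recognized to cause the event in question".

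Protocol 8.1.1 sets its own standard: a response is an adverse drug reaction when "a causal relationship between a medicinal product and an AE is at least a reasonable possibility, ie the relationship cannot be ruled out".

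On the setting, Protocol 2.1 states: "The primary objective is to assess the interaction between ADX-629 and ethanol". On Day 1 of each period, per Protocol 3.1, "1 dose of study drug will be administered at approximately 4:30 pm followed by standardized ethanol consumption". A second dose at about 7 pm is followed by more ethanol, up to a target blood alcohol concentration (BAC) of 0.14 g/100 mL.

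SAP 3.5.1 tabulates study-drug-related treatment-emergent AEs (TEAEs) overall, by maximum severity, and by system organ class and preferred term. The SAP text available gives no causality definition of its own.

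**The concern.** A two-category scale works only if every event falls into exactly one category. Here each category needs two conditions to hold together, and the two definitions are not complements. The case left out is an event that could be due to the drug but also has another identified cause.

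In many trials that case is uncommon. In this one it is built into the design, because ethanol is given after study drug to subjects selected for a history of alcohol-related symptoms. Nausea after the 7 pm dose is an example: its timing fits study drug, and the note to inclusion criterion 4 lists nausea as alcohol-related. The rater must still tick Yes or No, and the protocol supports either answer depending on which sentence is read.

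Two things are at stake. The counts of drug-related TEAEs depend on which text the rater follows. And an AE that arises from the drug-ethanol interaction, the subject of the primary objective, may be coded not related if ethanol is read as an other cause.

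**Working it through.** No sample size, power or event figure is involved, so this is a check of logic and of text against text.

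**Step 1. Which cases are covered.** Assume that timing either is compatible with the drug or rules it out. Yes turns on a cause being identified and No on a cause being suspected, so other cause is split into three levels: 2 × 3 = 6 combinations.

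| Timing | Other cause | Category met |
|---|---|---|
| Compatible | None | Yes |
| Compatible | Suspected, not identified | Yes |
| Compatible | Identified | Neither |
| Rules drug out | None | Neither |
| Rules drug out | Suspected, not identified | No |
| Rules drug out | Identified | No |

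No combination meets both definitions, and 2 of 6 meet neither. If suspected and identified are merged into one level, the result is 2 of 4. The fourth row would be coded No by any sensible rater. The third row is the one that matters.

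**Step 2. Does other text settle the third row?**

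- The Yes label admits *possibly*, which is wider than its definition and points to Yes.
- The No label admits *unlikely*, which is wider than timing that rules the drug out. It lets a rater who thinks ethanol the likelier cause choose No.
- The reasonable-possibility sentence and 8.1.1 point to Yes.
- The concomitant-drug factor tells the rater to look for another cause, but not how to code the event once one is found.
- No sentence says which of these texts governs.

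**Step 3. How often the design creates the situation.**

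- Doses per period: about 4:30 pm and 7 pm on Day 1, each followed by ethanol, and about 8 am on Day 2. So 2 of 3 doses per period, and 2 × 2 = 4 of 3 × 2 = 6 per subject, are followed by ethanol.
- After the 8 am dose, symptoms are still assessed at about 10 am and 1 pm, which is 2 h and 5 h later.
- The note to inclusion criterion 4 names 8 alcohol-related symptoms: headache, flushing, fatigue, diarrhea, nausea, dizziness, confusion/disorientation and nystagmus.

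These counts describe opportunity. They do not measure misclassification. Protocol 8.1 also prefers a syndrome to separate symptoms as the AE term, so eight symptoms need not mean eight causality calls.

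**Step 4. What uses the call.** The SAP 3.5.1 overview has 8 rows, of which 1 (study-drug-related TEAEs) depends on causality, together with its system organ class and preferred term table. Counts of all TEAEs and of serious AEs (SAEs), and the symptom scales, do not.

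**Step 5. Regulatory and unblinding uses.**

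- Protocol 8.3 requires every SAE up to 30 days after the last dose to be reported whatever its cause. Only later ones depend on relatedness. Thirty days is 30 × 24 = 720 h. At the longest mean half-life in Protocol 1.1.2, 6.83 h, that is 720 / 6.83 ≈ 105 half-lives, and BAC must be zero before discharge. Compatible timing with ethanol as a rival cause is not plausible by then.
- Protocol 8.5 has the sponsor or designee report suspected unexpected serious adverse reactions (SUSARs). Section 8.1.1 defines a reaction by the lower standard, and no text makes the 8.1.3 call the gate.
- Protocol 5.4 makes emergency unblinding turn on the subject's management and welfare. The yes/no call is recorded beforehand, and the remark on causally related events is general guidance.

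**The case against.** The strongest reply is that the two sentences were never meant as an algorithm. Taken together, the labels span the whole range from unrelated to definite, the listed factors call for judgment, and an experienced investigator will place a mixed event by label. Part of this stands: many raters will do so. But 8.1.3 directs that relatedness be assessed by the definitions, and the labels do not settle the case. An event that is probably due to ethanol and possibly due to the drug fits *unlikely* for one rater and *possibly* for another.

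A second reply concerns interaction AEs. A reader might infer that the Yes definition excludes them outright, since ethanol is always part of an interaction. The documents do not support that. An other cause can equally mean an explanation in place of the drug, and in an interaction the drug is itself a cause. The supportable statement is that such events may be coded not related under one reading.

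A third reply is that the safety-critical uses are protected. A reader might infer that SAE or SUSAR reporting, or unblinding, is compromised. Step 5 shows that the effect there is minor or indirect, and this reply stands.

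Finally, the eCRF completion procedures (Protocol 11.4) and the Study Procedures Manual are not among the documents and may say how ethanol effects are coded. If so, the practical effect shrinks, but the protocol text would still contradict itself.

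**Conclusion.** The point holds as a defect in a stated rule. The definitions in 8.1.3 leave unclassified an AE with compatible timing and an identified other cause, and they conflict with their own labels, with the sentence that follows them, and with 8.1.1. Because ethanol follows both Day 1 doses in each period, such events are expected.

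Its reach is one of eight overview rows and the matching system organ class and preferred term table. The effect on those counts cannot be estimated, because the documents give no AE rate under ethanol and no share of mixed-cause events.

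A reader might also infer a bias in favor of ADX-629. Nothing supports this: raters are blinded, there is one center, and each subject drinks ethanol in both periods of the crossover.

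The conclusion rests on two assumptions: that the study ethanol can count as an other cause (the parenthetical list of examples is open-ended), and that no unseen procedure overrides the protocol text. It should be corrected, but it does not threaten the trial's main comparisons.

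**What to change.** Reword the two definitions in Protocol 8.1.3 so that they are exhaustive, mutually exclusive and consistent with 8.1.1:

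- **Yes:** there is a reasonable possibility that study drug caused or contributed to the event, even if another cause such as ethanol could also explain it.
- **No:** there is no such reasonable possibility.

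Bring the eCRF completion procedures into line with this wording. SAP 3.5.1 needs no change.

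The edit is two sentences, but it is a protocol amendment and goes through the review and IRB approval described in Protocol 12.1. More events will probably be classed as related, in ADX-629 and placebo periods alike, so the related-TEAE row will discriminate less. A separate yes/no item for attribution to ethanol could offset that, but it is not needed to close the gap.
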